#### 11.1.6. Serious Adverse Reaction (SAR)

A serious adverse reaction is an SAE that is suspected as having a causal relationship to the investigational medicinal product, as assessed by the investigator responsible for the care of the patient. A suspected causal relationship is defined as possibly, probably or definitely related (see definitions of causality table).

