# 11.1.7. Definitions of causality

Relationship	Description
Unrelated	There is no evidence of any causal relationship with the trial treatment
Unlikely	There is little evidence to suggest there is a causal relationship (e.g. The event
	did not occur within a reasonable time after administration of the trial
	medication). There is another reasonable explanation for the event (e.g. The
	patient's clinical condition, other concomitant treatment)
Possible	There is some evidence to suggest a causal relationship (e.g. Because the event
	occurs within a reasonable time after administration of the trial medication).
	However, the influence of other factors may have contributed to the event (e.g.
	The patient's clinical condition, other concomitant treatments)
Probable	There is evidence to suggest a causal relationship, and the influence of other
	factors is unlikely
Definitely	There is clear evidence to suggest a causal relationship, and other possible
	contributing factors can be ruled out
Not assessable	There is insufficient or incomplete evidence to make a clinical judgement of the
	causal relationship.

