# 11.1.8. Suspected Unexpected Serious Adverse Reaction (SUSAR)

A serious adverse reaction, the nature or severity of which is not consistent with the safety information provided in the applicable Summary of Product Characteristics (SmPC), and is assessed as unexpected by the Chief Investigator.

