## 11.3. Reporting SAEs, AESIs, special situations and product complaints to ICR-CTSU

Any SAE, AESI, occurring after the commencement of study treatment and up to 90 days following the last dose of study drug must be reported. Special situation or product complaints should be reported when the investigator becomes aware of the incident.

Any SAEs that occur more than 90 days after the last dose of study drug that, in the opinion of the Principal Investigator, are related to the study drug should be reported to ICR-CTSU if the Principal Investigator becomes aware of them.

All SAEs, AESIs, special situations or product complaints should be reported to ICR-CTSU within 24 hours of the Principal Investigator (or designated representative) becoming aware of the event, by completing the relevant RE-ARM SAE/AESI/other incident form (as applicable).

SAE reports should be sent to:

The ICR-CTSU safety desk

[contact]

copying [contact]

For the attention of the RE-ARM Trial team

As much information as possible, including the Principal Investigator's assessment of causality for SAE reports, must be reported to ICR-CTSU in the first instance. Additional follow up information should be reported as soon as it is available.

All SAE forms must be completed, signed and dated by the Principal Investigator or designated representative. All reported SAEs will be forwarded to Roche by ICR-CTSU.

All reported AESIs, special situations and product complaints should be sent to [contact] and will be forwarded to Roche following receipt at ICR-CTSU.

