#### 11.4. Review of serious adverse events

The Chief Investigator (or designated representative) will assess all reported SAEs for causality and expectedness (NB. The Chief Investigator cannot down-grade the Principal Investigator's assessment of causality.)

SAEs assessed as having a causal relationship to study drug and as being unexpected (SUSARs) will undergo expedited reporting to the relevant authorities and all other interested parties by ICR-CTSU (see 11.5).

Sites should respond as soon as possible to requests from the Chief Investigator or designated representative (via ICR-CTSU) for further information that may be required for final assessment of an SAE.

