#### Secondary endpoints

Objective response rate according to iRECIST and clinical benefit according to RECIST v1.1 will be compared between trial arms as per the primary endpoint. Best response will be tabulated according to trial arm.

Duration of response, time to progression, progression free survival and overall survival will be presented according to trial arm using Kaplan-Meier survival plots and analysed using log-rank tests and Cox proportional hazards models. Rates of progression free and overall survival will be estimated at 12 and 24 months.

Treatment-related toxicity will be presented according to grade and trial arm.

Quality of life data will be analysed using standard algorithms to derive scores and handle missing data according to the questionnaire's scoring manual. The primary outcome measure for patient reported quality of life will be overall quality of life measured by the EORTC QLQ-C30 global health/quality of life subscale score, which will be treated as a continuous variable. Subscale scores will be compared between treatment groups at individual time points, as well as the change from baseline to Week 9 and 6 months, using ANCOVA adjusting for baseline scores. Additional analyses of EORTC QLQ-C30 subscales will dichotomise change in subscale scores from baseline to each follow-up timepoint according to whether or not patients have experienced a deterioration of >10 points, and compared between groups using chi-squared tests or Fisher's exact test, as appropriate. Analyses to account for the longitudinal nature of the data (generalised estimating equations) may also be used. Secondary QoL outcomes of interest include the EORTC QLQ-C30 subcales for physical functioning, role functioning and fatigue, individual domains and utility scores from the EQ-5D-5L.

QoL sub-study patients who are still being treated with atezolizumab at 12 months will be asked to complete the questionnaire at this timepoint. QoL data for this subset of patients will be compared with their baseline QoL data taking into account relevant covariates including other treatments taken, to explore the impact of long term use of atezolizumab on QoL.

Exploratory analyses will be conducted to investigate whether response varies according to site of target lesion. Details will be specified in the Statistical Analysis Plan.

Analyses of efficacy outcomes will be by intention-to-treat; safety analyses will be in the per protocol population.

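### An SAE graded Not assessable has no assigned route to SAR or SUSAR reporting when neither reviewer positively suspects a relationship

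*Protocol*

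**What the plan says.** Section 11.1.7 of the protocol offers six causality grades: unrelated, unlikely, possible, probable, definite and *Not assessable*. The last is described with the words "There is insufficient or incomplete evidence to make a clinical judgement of the" causal relationship, and no handling rule is attached to it.

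Section 11.1.6 defines a serious adverse reaction as an SAE with a suspected relationship to the investigational product, "as assessed by the investigator responsible for the care of the patient". It then closes the list and points to the table: "A suspected causal relationship is defined as possibly, probably or definitely related".

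The later steps depend on that status. Section 11.1.8 makes a SUSAR a kind of SAR: "A serious adverse reaction, the nature or severity of which is not consistent with the safety information provided". Section 11.4 says: "SAEs assessed as having a causal relationship to study drug and as being unexpected (SUSARs) will undergo expedited reporting". Figure 3 has two exits. If both the site investigator and the Chief Investigator suspect the event is unrelated, reporting ends. If either suspects it is related, expectedness is assessed. Section 11.6 sets 7 days for fatal or life-threatening SUSARs and 15 days for others, both counted from notification of the event to the trials unit.

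Other provisions apply whatever the causality grade. Section 11.3 states "All SAEs, AESIs, special situations or product complaints should be reported to ICR-CTSU within 24 hours" and "All reported SAEs will be forwarded to Roche by ICR-CTSU". Under 11.4 the Chief Investigator or a delegate assesses every SAE for causality and expectedness and may not lower the site's grade.

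**The concern.** A grade that investigators may use is missing from the rule that turns grades into reporting status. The grade is meant for events with too little information, and 11.3 asks for the site's causality opinion with the first report, when information is thinnest. If such an event is serious and unexpected, the rule as written does not class it as a SAR, and only a SAR can be a SUSAR. At stake is timely expedited reporting to the regulator and ethics committee, and inclusion in the annual SAR report. The trial's efficacy analysis is not affected.

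**Working it through.** No arithmetic beyond a count applies, and the plan has no figure to reproduce. The check sets the rules side by side and follows each combination of opinions.

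**Inputs.** The list of related grades (11.1.6), the six grades (11.1.7), the dependence of SUSAR on SAR (11.1.8), the Chief Investigator's review (11.4), the clocks (11.6) and the two exits (Figure 3).

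**Step 1: reduce the grades.** Possible, probable and definite are *related* (R). Unrelated and unlikely are taken as *not related* (U). This is an assumption, since Figure 3 speaks only of suspecting that the event is unrelated, but it follows from 11.1.6 leaving *unlikely* off its list. *Not assessable* is N.

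**Step 2: route each pairing through Figure 3.** Two reviewers with three states each give 3 × 3 = 9 pairings.

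| Site / Chief Investigator | Count | Route in Figure 3 |
|---|---|---|
| R/R, R/U, R/N, U/R, N/R | 5 | Either suspects related: expectedness assessed |
| U/U | 1 | Both suspect unrelated: reporting ends |
| N/U, U/N, N/N | 3 | Neither exit applies |

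5 + 1 + 3 = 9. The count shows where the gap lies. It says nothing about how often each pairing occurs.

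**Step 3: apply the definitions to the three unrouted pairings.** No reviewer has given a grade on the 11.1.6 list, so the event is not a SAR. By 11.1.8 it is then not a SUSAR. The 11.4 trigger also fails, because nobody has assessed the event as causally related.

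**Step 4: ask whether another rule supplies a default.**

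- The bar on down-grading presupposes an order of grades. *Not assessable* has no stated rank, so the text does not say whether moving from it to *unlikely* is a down-grade.
- Sites are to answer queries as soon as possible (11.4) or immediately (Figure 3). Neither gives a limit in days or says how the event is classified while the query is open. The clocks in 11.6 run from notification, not from the final assessment.
- Forwarding all SAEs to the drug supplier is a separate channel. Reporting to the regulator and ethics committee depends on SAR or SUSAR status.

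No default is found.

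**The case against.** The strongest reply is that the site's grade does not settle the matter. The Chief Investigator reviews every SAE, nothing bars raising the grade, and 11.6 ties expedited reporting to the Chief Investigator's identification of a SUSAR. Figure 3 ends reporting only when both reviewers suspect the event is unrelated, and *Not assessable* is not that judgement. This stands. A reader might infer that such an event can never become a SUSAR; the documents do not support that, because one reviewer's suspicion is enough.

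A second reply is that few events would be left in this grade. The table gives timing relative to dosing as an example of evidence for *possible*, so many unexplained on-treatment events could be placed there, and queries and follow-up add information. This stands as a point about frequency. It does not assign the grade: *possible* requires some evidence, and the table keeps a separate grade for insufficient evidence.

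A reader might also infer that these events drop out of the toxicity comparison, since "Treatment-related toxicity will be presented according to grade and trial arm". That does not follow. Neither 12.3.2 nor 12.4 sets a causality cut-off for toxicity or refers to 11.1.6, which covers only serious events and only the investigational product. The counting rule may properly sit in the SAP, which is not shown. No bias between arms and no effect on a reported rate can be claimed.

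Lastly, handling the grade as related is one convention, and the protocol does not require it. That is true. What the text needs is some stated default, and this one avoids losing an event through lack of information.

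**Conclusion.** The concern holds in a limited form. Sections 11.1.6 and 11.1.7 do not match, and 11.4 and Figure 3 do not repair the mismatch. The gap is confined to SAEs where neither reviewer suspects a relationship and at least one cannot judge. Read literally, these are not SARs and can miss annual SAR reporting and, if unexpected, the 7-day or 15-day clock. They are still reported within 24 hours, reviewed and forwarded to the supplier.

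The number of events cannot be estimated from the documents. The conclusion rests on the literal wording of the definitions and on treating *unlikely* as not related; a trials unit may already apply a default in practice that the protocol does not record. It is a cheap improvement to safety reporting, with no bearing on the sample size or the primary analysis.

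**What to change.** State in 11.1.6, 11.4 and Figure 3 that an SAE graded *Not assessable* by either reviewer, with neither grading it as related, is handled as related for SAR and SUSAR purposes until it is reassessed. The three places and the table in 11.1.7 will then agree. No change to the toxicity analysis is called for on this ground.

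The cost is about one sentence in each place and possibly a few additional expedited reports that are later reclassified as information arrives.

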# 11.1.7. Definitions of causality

Relationship	Description
Unrelated	There is no evidence of any causal relationship with the trial treatment
Unlikely	There is little evidence to suggest there is a causal relationship (e.g. The event
	did not occur within a reasonable time after administration of the trial
	medication). There is another reasonable explanation for the event (e.g. The
	patient's clinical condition, other concomitant treatment)
Possible	There is some evidence to suggest a causal relationship (e.g. Because the event
	occurs within a reasonable time after administration of the trial medication).
	However, the influence of other factors may have contributed to the event (e.g.
	The patient's clinical condition, other concomitant treatments)
Probable	There is evidence to suggest a causal relationship, and the influence of other
	factors is unlikely
Definitely	There is clear evidence to suggest a causal relationship, and other possible
	contributing factors can be ruled out
Not assessable	There is insufficient or incomplete evidence to make a clinical judgement of the
	causal relationship.

# 11.1.8. Suspected Unexpected Serious Adverse Reaction (SUSAR)

A serious adverse reaction, the nature or severity of which is not consistent with the safety information provided in the applicable Summary of Product Characteristics (SmPC), and is assessed as unexpected by the Chief Investigator.

# 11.2. Reporting adverse events to ICR-CTSU

Any toxicity, sign or symptom that occurs after commencement of study treatment and within 30 days of the last administration of study treatment, which is not unequivocally due to progression of disease, should be considered an AE. Out of range laboratory values should only be reported as AEs if they are clinically relevant (i.e. indicative of a clinical sign or symptom). The sign/symptom should be reported as the AE and the associated laboratory value provided as additional information where relevant.

All AEs must be reported on the relevant CRF and submitted to ICR-CTSU.

The severity of AEs should be graded according to CTCAE v5. For each AE, the highest grade observed since the last visit should be reported.

Whenever one or more toxicity/sign/symptom corresponds to a disease or a well-defined syndrome only the main disease/syndrome should be reported.

## 11.3. Reporting SAEs, AESIs, special situations and product complaints to ICR-CTSU

Any SAE, AESI, occurring after the commencement of study treatment and up to 90 days following the last dose of study drug must be reported. Special situation or product complaints should be reported when the investigator becomes aware of the incident.

Any SAEs that occur more than 90 days after the last dose of study drug that, in the opinion of the Principal Investigator, are related to the study drug should be reported to ICR-CTSU if the Principal Investigator becomes aware of them.

All SAEs, AESIs, special situations or product complaints should be reported to ICR-CTSU within 24 hours of the Principal Investigator (or designated representative) becoming aware of the event, by completing the relevant RE-ARM SAE/AESI/other incident form (as applicable).

SAE reports should be sent to:

The ICR-CTSU safety desk

[contact]

copying [contact]

For the attention of the RE-ARM Trial team

As much information as possible, including the Principal Investigator's assessment of causality for SAE reports, must be reported to ICR-CTSU in the first instance. Additional follow up information should be reported as soon as it is available.

All SAE forms must be completed, signed and dated by the Principal Investigator or designated representative. All reported SAEs will be forwarded to Roche by ICR-CTSU.

All reported AESIs, special situations and product complaints should be sent to [contact] and will be forwarded to Roche following receipt at ICR-CTSU.

#### 11.4. Review of serious adverse events

The Chief Investigator (or designated representative) will assess all reported SAEs for causality and expectedness (NB. The Chief Investigator cannot down-grade the Principal Investigator's assessment of causality.)

SAEs assessed as having a causal relationship to study drug and as being unexpected (SUSARs) will undergo expedited reporting to the relevant authorities and all other interested parties by ICR-CTSU (see 11.5).

Sites should respond as soon as possible to requests from the Chief Investigator or designated representative (via ICR-CTSU) for further information that may be required for final assessment of an SAE.

# 11.5. Expected Radiotherapy Adverse Events

The following adverse event will be classed as expected within the RE-ARM trial if they are assessed as being related to radiotherapy: fatigue; nausea/vomiting; diarrhoea; skin irritation/reaction; skin atrophy; mucositis; gastritis; colitis; shortness of breath; dysurea frequency.

The above listed events should be reported within the trial CRF database and under the reporting timeframes given for SAEs above if it meets the relevant reporting criteria.

#### 11.6. Expedited reporting of SUSARs

If an SAE is identified as being a SUSAR by the Chief Investigator, and is fatal or life threatening, it will be reported by ICR-CTSU to the MHRA, the main REC, Roche and all other interested parties within 7 days of being notified of the event.

If an SAE is identified as a SUSAR by the Chief Investigator, and is not fatal or life threatening, it will be reported by ICR-CTSU to the MHRA, the main REC, Roche within 15 days of ICR-CTSU being notified of the event.

ICR-CTSU will report any additional relevant information to the MHRA, main REC and Roche as soon as possible, or within 8 days of the initial report of a fatal/life threatening SUSAR.

The Principal Investigators at all actively recruiting sites will be informed of any SUSARs occurring within the trial at appropriate intervals.

#### 11.7. Follow up of serious adverse events

SAEs should be followed up until clinical recovery is complete or until disease has stabilised. SAE outcomes should be reported to ICR-CTSU using the relevant section of the SAE form as soon as the Principal Investigator or designee becomes aware of the outcome.

# 11.8. Annual reporting of serious adverse reactions

An annual report will be provided to the MHRA and the main REC by ICR-CTSU at the end of each reporting year.

## 11.9. Reporting pregnancies

Pregnancy is considered a special situation for the purposes of RE-ARM and should be reported in accordance with the above SAE reporting timelines. If any trial participant or a trial participants' partner becomes pregnant while receiving study drug or up to five months after receiving study drug, this should be reported to ICR-CTSU using the pregnancy reporting form. Participants who become pregnant should discontinue from trial treatment immediately. Pregnancies should be followed up until conclusion and all follow-up information should be reported to ICR-CTSU. If the outcome of the pregnancy meets the definition of serious (i.e. congenital abnormality) this should be reported to ICR-CTSU following the serious adverse event reporting procedures described above.

Adverse event observed in trial participant Responsibilities of Participating Centre Adverse event considered serious as Nο defined by the trial protocol? **IMMEDIATE REPORTING** Is the event an AESI? COMPLETE TRIAL SPECIFIC SAE/AESI FORM\* Νo No immediate reporting Submit form to ICR-CTSU within 24 hours of becoming required - record on aware of the event relevant CRF Sites must respond immediately to Receipt of SAE/AESI acknowledged by ICR-CTSU requests for further information for CI personnel and any missing / unclear data queried review/Roche reporting All reported AESIs will be forwarded to Roche ICR-CTSU forward SAE to the Chief Investigator (CI) or All reported SAEs will be forwarded to nominated representative for assessment of Roche following assessment by the relatedness and expectedness. Report is returned to the Chief Investigator Responsibilities of Sponsor as per Agreement ICR-CTSU once assessment is complete. **Both** the PI and CI PI and/or CI suspects suspect SAE is unrelated SAE is related CI (or nominated No further reporting representative) required SUSARs will be reported assessment of by ICR-CTSU to: expectedness of the • MHRA and Main REC within 7 SAR calendar days (15 days if non fatal or Expected Unexpected non life threatening) of initial report, as per regulations Sponsor institution SUSAR • Principal investigators at regular SAR Requires expedited intervals ICR-CTSU report all SARs reporting to Main REC and MHRA annually. Sponsor **SUSAR Follow Up** institution also notified Additional relevant information at agreed timelines reported to MHRA, Main REC and Sponsor as soon as possible or within 8 days of initial report if fatal/life threatening

Figure 3: Flow diagram for AE reporting, and action following report

All SAEs should be followed up until resolution.

\*If any AESI also meets the definition of an SAE, an SAE report should be completed and submitted together with the AESI form

#### 12. STATISTICAL CONSIDERATIONS

## 12.1. Statistical design and sample size justification

The trial design is an adaptive 2-arm randomised group-sequential design with a formal interim assessment to stop recruitment early if the number of responses in the experimental arm is not higher than in the control arm.

In the IMvigor210 study a response rate of 17% was reported in patients who initially progressed. To detect an absolute increase of at least 15% in response rate at 9 weeks for the experimental arm compared with the control arm (assuming 15% response in control, 1:1 randomisation) with 80% power using a 1-sided z-test with 0.2 significance level requires 92 evaluable patients. An interim analysis will take place when 23 patients per arm have completed the 9 week primary endpoint response assessment with a formal stopping rule that the trial will close to recruitment if the z-test statistic is not higher than the futility boundary of 0 (i.e. if there are not more responses in experimental arm versus control). The futility boundary for the final analysis is 0.68.

Allowing for a 10% non-evaluable rate at 9 weeks gives a planned overall sample size of 102 patients. The non-evaluable rate will be monitored during the trial; any major departures requiring adjustment to the overall sample size required to recruit 92 evaluable participants will be discussed with the independent oversight committees.

The required sample size calculations were performed using the group sequential testing option in nQuery + nTerim v4.0 and in-house written R-codes. The bespoke R-codes were required in order to amend the futility boundaries so that the boundary at the interim analysis is 0 (i.e. requiring at least 1 more response in the experimental arm versus control).

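### Boundaries of 0 (interim) and 0.68 (final) do not secure the stated one-sided 0.2 level: 21.7% by normal theory; by exact calculation 19.65% at a 15% response rate, but up to 21.6% at other rates

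*Protocol*

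**What the plan says.** All the design figures stand in Protocol section 12.1. The target is stated as follows: "To detect an absolute increase of at least 15% in response rate at 9 weeks for the experimental arm", compared with control, "assuming 15% response in control, 1:1 randomisation". The operating characteristics are given as "with 80% power using a 1-sided z-test with 0.2 significance level requires 92 evaluable patients", which is 46 per arm.

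On the interim the section says: "An interim analysis will take place when 23 patients per arm have completed the 9 week primary endpoint response assessment". Recruitment then closes unless the z statistic is above 0. The section restates this in counts: the experimental arm must have at least one more response, so a tie stops the trial.

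On the final analysis it says: "The futility boundary for the final analysis is 0.68".

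The calculations used nQuery and in-house R code: "The bespoke R-codes were required in order to amend the futility boundaries so that the boundary at the interim analysis is 0". The section does not say whether the 0.2 level was checked by normal approximation or by exact calculation on response counts, and it does not state the level achieved.

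**The concern.** The final boundary decides whether radiotherapy is judged to have improved response. In a two-stage design with a futility stop, the final boundary, the interim boundary and the timing of the interim together fix the type I error. Here all three are stated, so the level can be recomputed.

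The standard group-sequential calculation does not return 0.2. If the stated level is not the one the rule delivers, a positive result would be reported against a stricter error rate than the design has.

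**Working it through.** **Inputs (all from section 12.1).** One-sided level 0.2; power 80%; 15% against 30%; 1:1 allocation; interim at 23 of 46 per arm, an information fraction of 0.5; continue only if Z1 > 0; positive at the end if Z2 > 0.68. The stopping rule is taken as always followed, because the protocol calls it formal.

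**1. The plan's sample size, by normal theory.**
- Pooled rate: (0.15 + 0.30)/2 = 0.225.
- Standard error at 46 per arm: sqrt(2 × 0.225 × 0.775 / 46) = 0.0871.
- Expected final z: 0.15/0.0871 = 1.72. Expected interim z: 1.72 × sqrt(0.5) = 1.22.
- P(Z1 > 0 and Z2 > 0.68), with correlation sqrt(0.5): 80.4% (81.2% with unpooled variance).
- With pooled variance, 46 per arm is the smallest size that reaches 80% (45 per arm falls just short). The stated 92 and 80% are therefore reproduced with boundaries 0 and 0.68.

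**2. The level, by normal theory.** Under no effect and with correlation sqrt(0.5), P(Z1 > 0 | Z2 = z) = Φ(z). Hence

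P(Z1 > 0, Z2 > c) = ∫ from c to ∞ of φ(z)Φ(z) dz = (1 − Φ(c)²)/2.

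- At c = 0.68: Φ = 0.7517, so (1 − 0.7517²)/2 = 0.217.
- For 0.20: Φ(c) = sqrt(0.6) = 0.7746, so c = 0.754.

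**3. The level, by exact calculation.** All outcomes of 23 + 23 patients per arm were enumerated, with ties stopping at the interim and a pooled z above the final boundary counted as positive.

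| Common response rate | Level with 0.68 | Level with 0.754 |
|---|---|---|
| 15% | 19.65% | 19.0% |
| 17% | 20.15% | 19.4% |
| 20% | 21.0% | 19.3% |
| 23% | 21.5% | 18.7% |
| 25% | 21.6% (maximum) | 18.4% |
| 30% | 20.8% | 18.3% |
| 35% | 19.7% | 18.9% |

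With 0.68 the level is above 20% for common rates of about 16.5% to 33%. With 0.754 it stays below 20% at every rate checked from 5% to 50% (maximum 19.65%).

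**4. Why the two methods differ at 15%.** Most of the gap comes from the interim ties. If ties continued, the exact level at 15% with 0.68 would be 22.3%. The rest is discreteness: at 15% the exact level is 20.55% for a boundary just below 0.67, and 19.65% from 0.67 to about 0.74.

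**5. Power for 15% against 30% at 46 per arm.**
- Boundary 0.68: 79.5% exact.
- Boundary 0.754: 77.7% exact; 79.1% (pooled) to 79.8% (unpooled) by normal theory. Reaching 80% by normal theory would take 47 to 48 per arm, or 94 to 96 evaluable patients.

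**The case against.** The strongest reply is that the written rule is a rule about counts, and that at the protocol's own 15% rate it meets its claim: 19.65% level and 79.5% power against a stated 20% and 80%. The 21.7% belongs to an approximation, and exact calculation did not reach it at any common rate examined. Moreover, 0.68 lies just inside the range of boundaries that keeps the exact level below 0.2 at 15%, so it may have been chosen by a count-based calculation. All of this stands.

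It can also be said that the level of any z-test on binary data is approximate. A single-stage pooled z-test at 0.8416 with 46 per arm has an exact level of 21.4% at a 15% rate. That stands too, and it limits the seriousness. The practical reach is small as well: with up to 46 responses in total, only five final results fall between 0.68 and 0.754 (5 v 3, 12 v 9, 13 v 10, 14 v 11 and 15 v 12).

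The reply does not remove the point. The null response rate is unknown, and modest departures from 15% take the exact level above 0.2. Section 12.1 itself cites 17%, although for an external group who had initially progressed. The section states 0.2 without any condition on the rate.

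**Conclusion.** The point holds in a limited form. Boundaries of 0 and 0.68 meet the 0.2 level by exact calculation at the assumed 15% rate. They do not meet it by normal theory (21.7%), nor exactly for common rates of about 16.5% to 33% (at most 21.6%). The excess is at most 1.7 points, which is modest for a phase II trial designed at a 0.2 level. It deserves correction because it concerns the primary decision threshold and is cheap to put right.

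The result assumes that the interim rule is always followed, that ties stop the trial, that there are 23 and then 46 evaluable patients per arm, and that the final statistic is a pooled z.

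Two stronger readings are tempting and not supported. A reader might infer that the design's level simply is 21.7% and that 0.68 is an error; the exact result at 15% contradicts that. A reader might also infer from the mention of amended boundaries that 0.68 was left over from before the interim boundary was set to 0. The protocol does not show how 0.68 was derived, and a count-based derivation fits it as well.

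**What to change.** In section 12.1, keep 0.68 and the 92 evaluable patients. Restate the one-sided level as about 0.20 at a 15% common response rate and up to about 0.22 at other rates (21.7% by normal approximation), and say which method was used to derive the boundary. The cost is one or two sentences and a slightly less favourable stated level.

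Alternatively, if control at 0.2 is wanted whatever the common rate, replace 0.68 by 0.754 and restate power as about 78% exact (about 79% to 80% by normal approximation). The cost is about 2 points of exact power (79.5% to 77.7%) if 92 patients are kept.

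Either choice should be made before the final analysis and carried into the statistical analysis plan.
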